# **1.3** Secondary Objectives & Hypotheses

**Secondary Objective 1**: To estimate the 6-month progression-free survival (PFS6) in recurrent/progressive GBM participants treated with VB-111 (Group A and Group B) compared to control (Group C), using RANO criteria.

**Hypothesis 1:** We hypothesize that a greater percentage of participants who are treated with VB-111 will not have experienced tumor progression at 6 months after treatment.

**Secondary Objective 2:** To calculate the overall survival of recurrent/progressive GBM participants in each arm.

**Hypothesis 2:** We hypothesize that progressive/recurrent GBM participants treated with VB-111 will live significantly longer than Group C and/or historical controls of this participant population.

**Secondary Objective 3:** To evaluate the influence of VB-111 on peripheral T cell responses, specifically on expanded TCR clones.

**Hypothesis 3:** We hypothesize that specific subsets of TCR clones will expand in response to VB-111.

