## 5.1 Treatment Regimen

Participants will be screened for eligibility up to 14 days prior to randomization. They will be sequentially randomized to one of three groups in a 1:1:1 ratio of the Neoadjuvant/Adjuvant arm (Group A), Adjuvant arm (Group B), and Control arm (Group C).

Group A (Neoadjuvant/adjuvant): Fifteen participants will receive VB-111 at 1x10^13 VPs intravenously 21±7 days prior to surgery. Tumor samples will be obtained at time of surgery, and tissue (fresh, frozen and FFPE) will be processed to achieve primary, secondary and exploratory objectives. Upon recovering from surgery (within 28-35 days after surgery), participants will resume single agent intravenous VB-111 every 6 weeks until tumor progression is supported by two consecutive time points of tumor growth (based on RANO criteria) or adverse event requiring discontinuation of study drug. Upon initial evidence of contrast-enhancing progression, and if clinically stable, participants may continue with VB-111 infusions. Bevacizumab or biosimilar may be used as supportive care if clinically indicated. Blood samples will be obtained as pharmacodynamics markers throughout the study. Dose holds and symptomatic management will occur based on preset adverse event determination. DLTs will not be determined. The toxicity evaluation period will begin with registration and extend to 30 days after the last treatment day. Participants will be followed for MRI changes, clinical exam and steroid doses from the registration period until the second progression. After tumor progression is confirmed on the second consecutive MRI, VB-111 will stop and participants will be followed every 3 months for vital status until death.

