## **13.1.1 Efficacy Endpoints**

Tumor infiltrating T cell (TIL) density is defined as the number of T lymphocytes per nucleated cell, and calculated by detailed sequencing of recombined T cell receptor sequences obtained from the tumor specimen gDNA.

PFS6 is defined as the percentage of participants with progression-free survival at 6 months from surgery as defined by RANO.

OS is defined as the time from randomization until death from any cause. Participants will be followed for survival status after progression or discontinuation of the study drug for other reasons.

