## **13.2** Definitions of Analysis Sets

- The Full Analysis Set (FAS) population will serve as the population for the analysis of primary efficacy endpoint TIL density in this study. The FAS population consists of all participants within each cohort who have received a preoperative dose of VB-111/placebo and had a surgery.
- The intention to treat (ITT) population is defined as all randomized participants. The ITT population will be used for secondary efficacy endpoints (PFS6, OS).
- The All Participants as Treated (APaT) population will be used for the analysis of safety data in this study. The APaT population consists of all allocated participants who received at least one dose of study treatment. At least one laboratory or vital sign measurement obtained subsequent to at least one dose of study treatment is required for inclusion in the analysis of each specific parameter. To assess change from baseline, a baseline measurement is also required.

A randomized, placebo controlled phase II, surgical trial to evaluate early immunologic pharmacodynamic parameters for the viral cancer therapy ofranergene obadenovec (VB-111) in patients with surgically accessible recurrent/progressive glioblastoma Version 3.0 February 18, 2021

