## 13.3 Sample Size Consideration

This is a randomized, controlled, blinded, phase II, surgical trial to evaluate early immunologic pharmacodynamic parameters for the viral cancer therapy VB-111 in participants with surgically accessible recurrent/progressive glioblastoma (rGBM). Participants will be randomly assigned to group A or B or C with a 1:1: 1 randomization ratio prior to surgery. The primary hypothesis is that VB-111 can generate effective anti-tumor immune responses in the form of a statistically significant increase in TIL density comparing Group A (neoadjuvant/adjuvant) vs combined control group (Group B+C).

Based on our preliminary data, the mean of TIL density is estimated to be 0.4 (T cells per nucleated cell) (SD=0.5) in the combined control group (Group B and C). Comparing Group A vs Group B+C at an alpha level of 0.05 (1-sided) using a stratified two-sample t-test, a sample size of 30 in the combined Group (B+C), and 15 in Group A (Total of 45 evaluable) allows for the detection of a standard difference in TIL density of 0.8 or larger with 84% power. Effect size is defined as Cohen's D, the difference of two population means, divided by the pooled standard deviation. [63]

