## 13.4 Efficacy Analysis

A two-sample t-test with tumor size stratification will be used to test the difference of tumor infiltrating T cell density between the two groups (Group A vs combined Group B+C). Data distribution will be examined prior to analysis. Data transformations will be performed as deemed appropriate.

For the secondary endpoint of PFS6, historical comparison data are available from a pooled analysis of Phase II experience in recurrent Grade IV gliomas who have undergone surgery either just prior to starting treatment or as part of the protocol, which documented a PFS6 rate of 10%. Group comparisons (Group A vs C; Group B vs C; Group A+B vs C) will be conducted using the exact binomial test with Bonferroni adjustment to compare PFS6 rate at one sided alpha of 5%.

For OS, analyses will be conducted using historical comparison data which are available from a pooled analysis of Phase II experience in recurrent Grade IV gliomas who have undergone surgery either just prior to starting treatment or as part of. Kaplan-Meier (KM) curves and median estimates from the KM curves will be provided as appropriate. Participants without efficacy evaluation data or without survival data will be censored at Day 1. For evaluation of the expansion of TCR clones, a two-sample T-test with Bonferroni adjustment will be used to compare the increase number of expanded TCR clones after VB-111 in Group A+B vs Group C.

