# **13.6 Exploratory Analyses**

Variables involved in exploratory analyses will be examined graphically and summarized by descriptive statistics. Data transformation may be applied to quantitative variables prior to analyses if deemed necessary.

Bivariate association analyses will be conducted to evaluate the associations between exploratory biomarkers and clinical outcomes and adverse events for the objectives listed in 1.4. The analyses will be performed for each group separately and/or combined as deemed appropriate. Specifically, Pearson or Kendall's tau correlation coefficients will be calculated to evaluate the association between quantitative variables, Chi-squared tests or Fisher's exact tests will be used to examine the association between categorical or ordinal variables, and ANOVA will be performed to study the association between a quantitative variable and a categorical variable. The association between biomarkers and clinical outcomes (PFS and OS) will be evaluated using Cox regression and elastic net regularized regression for variable selection. For markers with multiple measurements over time, data at a specific time point or change from pre-treatment will be used in the above bivariate analyses as deemed appropriate.

Changes in markers pre- and post- treatment will be assessed using paired t-tests.

Between-group comparisons will be conducted for PFS, OS, TIL density, interferon and cell cycle-related genetic signatures, and IHC expression. Survival analyses via Kaplan-Meier curves and log-rank tests will be used to estimate and compare PFS, second PFS, and OS between Group A, Group B, and Group C.

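### The secondary OS analysis names only a historical comparator; the randomized comparison with Group C should take that place, with the historical series kept descriptive

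*Combined protocol and SAP*

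**What the plan says.** Section 5.1 has participants "randomized to one of three groups in a 1:1:1 ratio", with Group C as the control arm. Section 13.3 plans "a sample size of 30 in the combined Group (B+C), and 15 in Group A (Total of 45 evaluable"), which implies 30 in A+B and 15 in C.

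Hypothesis 2 (Section 1.3) is that participants given VB-111 "will live significantly longer than Group C and/or historical controls of this participant population". The objective above it is to calculate OS in each arm.

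Section 13.1.1 sets the clock: "OS is defined as the time from randomization until death from any cause". PFS6 in the same section is counted from surgery. Section 13.2 sets the population: "The ITT population will be used for secondary efficacy endpoints (PFS6, OS").

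Section 13.4 then gives the OS analysis: "For OS, analyses will be conducted using historical comparison data which are available from a pooled analysis of Phase II experience", the series being "recurrent Grade IV gliomas who have undergone surgery either just prior to starting treatment or as part of". The sentence breaks off there; the near-identical PFS6 sentence ends by referring to the protocol. Kaplan-Meier curves and medians follow. For OS the section states no test, alpha, benchmark value or historical time origin, and does not mention Group C. For PFS6 it lists A vs C, B vs C and A+B vs C, and for TCR clones A+B vs C.

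Section 13.6, on exploratory analyses, adds that "log-rank tests will be used to estimate and compare PFS, second PFS, and OS between Group A, Group B, and Group C".

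**The concern.** OS is the only one of the three secondary endpoints for which 13.4 leaves the randomized control out. The comparison that randomization protects is labelled exploratory, while the one given secondary status depends on an external series whose eligibility, benchmark and time origin the reader cannot check.

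Two kinds of bias could enter. The first is selection: Section 3 requires a longest diameter of at most 4 cm, KPS of at least 70, dexamethasone of at most 2 mg daily and no prior anti-angiogenic therapy, and nothing says the historical series was matched on these. The second is the clock. If historical survival is counted from a later event than randomization, trial participants are credited with extra time that has nothing to do with treatment. Between randomized arms that interval cancels.

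Status also matters for change control. Under the opening of Section 13, changes to primary or key secondary hypotheses or their methods need a protocol amendment, whereas changes to exploratory analyses are only listed in the study report.

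**Working it through.** The plan gives no OS sample size, event count, power, alpha or benchmark, so there is no OS figure to reproduce.

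**1. Length of the interval**
- Randomization to pre-operative dose: 0 to 5 days (5.3.1).
- Pre-operative dose to surgery: 21±7, so 14 to 28 days (5.1).
- Surgery to post-operative therapy: 28 to 35 days in all groups (5.1).
- Randomization to surgery: 0+14 = 14 to 5+28 = 33 days.
- Randomization to post-operative therapy: 0+14+28 = 42 to 5+28+35 = 68 days, or 6.0 to 9.7 weeks. If the ±3-day dosing window of 5.3.2 also applies to the first post-operative cycle, the range is 39 to 71 days.

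**2. Effect on the median, with no drug effect**
Assume survival from the later origin equals the historical curve. The stand-in median is 224 days, taken from the bevacizumab meta-analysis in Section 2.2.2, not from the series meant in 13.4. If everyone reaches the later origin, the apparent median is 224 + L:
- from post-operative therapy: 224+42 = 266 to 224+68 = 292 days;
- from surgery: 224+14 = 238 to 224+33 = 257 days.

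If a fraction q dies first and survival is exponential, the median is L + 224 × ln((1−q)/0.5)/ln 2. With q = 5% and L = 42 to 68 this gives 249 to 275 days. The shift disappears under a constant hazard from randomization, which needs q = 1 − 2^(−L/224), that is 12% at 42 days and 19% at 68 days.

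**3. Illustrative false-positive rate**
Assumptions, none of them in the plan's OS text: one-sample log-rank test with Z = (O−E)/√E, rejection at Z < −1.645 (the one-sided 5% is borrowed from PFS6), n = 30 (A+B), exponential survival, 18 months' follow-up, no drug effect. Simulated rejection rates:

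| Historical clock starts at | Offset, days | No earlier deaths | 5% die first |
|---|---|---|---|
| Randomization | 0 | 4% | – |
| Surgery | 14 to 33 | 6 to 11% | – |
| Post-operative therapy | 42 to 68 | 14 to 28% | 9 to 18% |

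The upper figure of 28% came out between 27 and 28% in repeated runs. The rates depend on the method. With variance (O+E)/2 the 9 to 18% becomes 11 to 22%. With that variance, 24 months' follow-up and a Weibull curve of shape 1.48 (set to the 24% alive at 12 months in Section 2.2.2), it becomes 18 to 39%.

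Selection cannot be sized from the documents. An arbitrary prognostic hazard ratio of 0.8, with aligned clocks and no drug effect, would give about 25%.

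**4. What the randomized comparison can deliver**
For A+B vs C at 2:1, the standard error of the log hazard ratio is about 1/√(d × 2/3 × 1/3), with d deaths.
- d = 45 (everyone dies): 1/√10 = 0.316, so 95% limits lie a factor exp(1.96 × 0.316) = 1.86 either side of the estimate. 80% power at one-sided 5% needs HR = exp(−(1.645+0.842) × 0.316) = 0.46.
- d = 30: 80% power needs HR of about 0.38.
- At HR 0.51, the earlier phase 2 estimate in Section 2.2.2, power is 69% with 45 deaths and 54% with 30.

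**The case against.** Hypothesis 2 says Group C and/or historical controls, so a historical comparison lies within the stated hypothesis, and the parent objective is estimation by arm. That stands: the weakness is that the historical series is the only comparator in the secondary analysis, not that it is used.

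A reader might infer that no randomized OS comparison is planned. Section 13.6 plans one across all three groups, so it would be reported; what is missing is its status, its main contrast and an effect estimate.

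A reader might also infer that the plan tests OS against history at 5%. Section 13.4 specifies no such test, so the rejection rates above describe an assumed analysis. Nor do the documents show that the historical comparison will create a benefit. Part of the historical series had surgery within a protocol, so its clock may start before surgery as here, and the offset could be nil. Intention-to-treat analysis counts deaths before surgery, which offsets some of any shift. The 224-day median is a stand-in, 18 months is an assumption (Section 5.1 follows participants until death), and the historical cohort's eligibility is unknown. For Group A, VB-111 starts within 5 days of randomization, so the 42 to 68 days run to post-operative therapy, not to first study drug.

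Finally, the trial was sized on TIL density, and an OS comparison with 15 controls is weak. That is true. It argues for reporting an estimate with its interval rather than for a comparator of unknown bias.

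**Conclusion.** The point holds as one of analysis status and missing specification. Section 13.4 rests the secondary OS analysis on a historical series alone, while a concurrent randomized control exists, is named in the hypothesis and serves as comparator for the other secondary endpoints. The historical comparison is exposed to selection bias and possibly to a clock mismatch of 14 to 33 days (if its clock starts at surgery) or 42 to 68 days (if at post-operative therapy).

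The amount of bias is unknown. The clock part is nil if the origins align. Under the stated stand-in assumptions the false-positive rate would be about 6 to 11% in the surgery case and about 14 to 28% in the post-operative case, or 9 to 18% if 5% die first. These figures show what is possible; they do not establish that a false benefit would be claimed. The change is worth making because it is cheap and removes both sources of bias from the secondary OS conclusion.

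**What to change.** In 13.4, make the intention-to-treat comparison with Group C the secondary OS analysis. Use A+B vs C as the main contrast, with A vs C and B vs C as supportive. Specify a log-rank test and a Cox hazard ratio with confidence interval, both stratified by baseline tumor size as in the randomization (5.5), and say that the result will be read mainly as an estimate because precision is low.

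Keep the historical comparison descriptive. Complete the broken sentence, state the series' OS benchmark and time origin, and re-time trial OS to that origin wherever the two are shown together.

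The cost is SAP wording; the between-group log-rank is already planned in 13.6. The downside is wide confidence limits, which the text should acknowledge.

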After recovering from surgery, participants will be evaluated every 6 weeks with radiographic imaging to assess response to treatment. The Response Assessment in Neuro-Oncology (RANO) criteria will be used as the efficacy endpoint of response rate. A modified RANO (iRANO) (as described in Section 11.4) will be used to evaluate response and progression in an exploratory fashion due to the tumor response patterns seen with immunotherapy treatment. Adverse events will be monitored throughout the trial and graded in severity according to the guidelines outlined in the NCI Common Terminology Criteria for Adverse Events (CTCAE) version 5.0. Treatment with study therapy will continue until progression is supported by two consecutive time points of tumor growth, unacceptable adverse event(s), intercurrent illness that prevents further administration of treatment, investigator's decision to withdraw the participant, participant withdraws consent, pregnancy of the participant, noncompliance with trial treatment or procedure requirements, completion of 24 months of study therapy, or administrative reasons. After the end of treatment, each participant will be followed for 30 days for adverse event monitoring and 90 days for serious adverse event reporting. Participants who discontinue treatment for reasons other than disease progression will have post-treatment follow-up of disease status until disease progression, withdrawing consent or becoming lost to follow-up. All participants will be followed by telephone contact or medical record review for overall survival until death, withdrawal of consent, or the end of the study, whichever comes first.

Our hypothesis is that a functional immune defect exists within the T lymphocyte compartment in recurrent/progressive glioblastoma participants, and the neoadjuvant use of VB-111 will lead to:

1) increased tumor infiltrating T lymphocytes within the tumor; and 2) enhanced systemic specific T cell responses. The combination of tumor tissue, peripheral blood, and imaging evaluations should provide insight into immune activation, antitumor effect and toxicity with VB-111 in this population.

Specific procedures to be performed during the trial, as well as their prescribed times and associated visit windows, are outlined in the Study Calendar in Section 9.

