- 8. A contact/visit is to be performed at 30 days (+7 days) after the last study drug is given. This may be performed via documented phone conversation with a study nurse or clinician or a clinic visit. All participants will be followed until resolution or stabilization of any serious or reportable adverse events occurring during treatment or starting within 30 days of last study drug.
- 9. For participants who discontinue study treatment for reasons other than disease progression, every effort should be made to continue monitoring their disease status by radiologic imaging at a schedule developed by the treating investigator until (1) documented disease progression, (2) death or (3) the end of the study, whichever occurs first.
- 10. Long Term Follow Up: participants will be followed every 3 months (+/- 1 month) via contact or medical record review until death for post-treatment therapies, reason for stopping those therapies and survival.
- 11. Informed Consent must be obtained by a delegated MD attending. No study specific screening procedures may occur until after the informed consent process is complete. Informed Consent may be obtained within 28 days of enrollment.
- 12. Background information/history is to include review of treatment history for GBM, any ongoing medical conditions and medical history pertaining to eligibility on study and involvement during study.
- 13. Inclusion/exclusion criteria: source documentation providing investigator's confirmation that the participant meets all eligibility criteria must be available prior to registration.
- 14. Vital signs include weight, heart rate, blood pressure, respiration rate, temperature. Vital signs must be performed prior to administration of treatment on treatment days. Height required only at screening.
- 15. Neurologic Exam is to be completed by the investigator or qualified designee at screening, and Day 1 of postsurgery treatment cycles.
- 16. Directed Physical Exam is to be completed at screening, pre-surgery treatment visit, Day 1 of post-surgery treatment cycles, and as clinically indicated by the investigator or qualified designee.
- 17. Performance Status is to be assessed by KPS (Appendix A).
- 18. Concomitant medications and reason for administration should be documented in the case history from date of consent up to the 30-Day Post Drug Visit. Concomitant medications administered after 30 days after the last dose of trial treatment should be recorded for SAEs.

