- 19. Adverse events experienced by participants will be collected and recorded from the first dose of study treatment up to the 30-Day Post Drug Visit of the last dose of study medication (+ 7 days depending on when 30-Day Post Drug visit/contact occurs) and all SAEs (related and unrelated to trial treatment) up to 90 days after the last dose of treatment. Afterwards, report only SAEs that are considered related to trial treatment. Adverse events may also occur in screened participants during pre-allocation baseline period as a result of a protocol-specific intervention, including washout or discontinuation of usual therapy, diet, placebo treatment or a procedure.
- 20. For women of child bearing potential, a urine pregnancy test must be performed. If urine pregnancy results cannot be confirmed as negative, a serum pregnancy test will be required.
- 21. PT/INR, PT, PTT are required at screening and PTT will be checked again with pre-surgery labs. Thereafter,

coagulation to be checked when clinically indicated.

- 22. Hematology includes erythrocytes (RBC), hemoglobin, hematocrit, platelets, total WBC plus differential (neutrophils, lymphocytes, monocytes, eosinophils, basophils).
- 23. Serum Chemistry includes albumin, alkaline phosphatase (ALP), bicarbonate (HCO3), BUN, calcium, chloride, creatinine, glucose, magnesium, potassium, SGOT (AST), SGPT (ALT), sodium, total protein, total bilirubin.
- 24. Virology panel includes Hepatitis A Antibody, Hepatitis B Core IgG and M Antibody (Anti-HBC, total), Hepatitis B Surface Antibody (Anti-HBs), Hepatitis B Surface Antigen (HBsAg), Hepatitis C Surface Antibody (anti-HCV), HIV-1/2 Ag/Ab and HTLV-1/2 Ag/Ab. If any hepatitis serology is positive, qualitative PCR for Hepatitis B DNA or Hepatitis C RNA will be obtained and results must be negative for eligibility.
- 25. Imaging: gadolinium-enhanced contrast and non-contrast MRI. Initial imaging should be performed within 14 days prior to enrollment. On-study imaging should be performed every 6 weeks starting from post-surgery treatment Cycle 1 Day 1. The same imaging technique should be used in a participant throughout the trial, if feasible. Local reading (investigator assessment) will be used to determine eligibility and for participant management.
- 26. Response Assessment to be completed per RANO criteria (Section 10).

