- 27. Pre-surgery VB-111/placebo administration is required for participants in all Groups 21±7 days prior to surgery. Group A and B will receive post-surgery VB-111 administration and it must start 28-35 days after surgery. Post-surgery VB-111 may be administered ±3 days from day 1 of each cycle. To avoid fever following study drug VB-111 administration, all patients will receive 1) 900-1000 mg of acetaminophen starting 1-2 hours prior to VB-111/Placebo dosing followed by 450-500 mg when necessary for up to 36 hours and 2) dexamethasone 4 mg 1-2 hours prior to VB-111/Placebo dosing followed by 4 mg for 3 days may be given if deemed necessary by the investigator.
- 28. Blood for biomarker evaluation: please see Table 4 Correlative Sample Summary for details on collection requirements.
- 29. Pre-study archival tumor tissue is to be submitted within 60 days of Randomization. Protocol surgery tissue is to be collected during the trial. Please see Table 4 Correlative Sample Summary for details on collection requirements.
- 30. Start/stop dates, names of treatment regimens and reason for stopping should be collected.
- 31. Date of death and reason should be collected for overall survival purposes, when applicable.
- 32. For all participants, if the post-surgery MRI is greater than 21 days from post-surgery VB-111 then MRI must be repeated on Cycle 1 Day 1. Starting from EOT visit, the participants will be followed up by radiologic imaging per standard of care.
- 33. The baseline research sample at the neoadjuvant time point must be drawn before treatment begins.
- 34. The Pre-Surgical Visit / Assessments will be done either on day of surgery or within 3 days prior to surgery.

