# **11. MEASUREMENT OF EFFECT**

Tumor response will be assessed every 6 weeks using contrast and non-contrast brain magnetic resonance imaging (MRI) with assessment based on the RANO criteria [55] until progression is supported by two consecutive time points of tumor growth (local and central blinded independent radiology review). For participants who do not progress or die, PFS will be censored at the last adequate radiologic assessment. Baseline scan for determining progression will be the post-operative scan obtained just prior to initiating post-operative therapy.

Clinicians may repeat response assessment more frequently as clinically indicated.

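### The only OS censoring sentence makes no exception for a known death: on one open reading of an undefined term, a participant who dies before any efficacy assessment is censored at Day 1

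*Combined protocol and SAP*

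**What the plan says.** The OS paragraph of Section 13.4 plans a comparison with historical data, Kaplan-Meier curves and medians, and one censoring rule: "Participants without efficacy evaluation data or without survival data will be censored at Day 1". No other sentence in the documents gives a censoring date for OS, and *efficacy evaluation data* is neither used elsewhere nor defined.

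The endpoint is defined in Section 13.1.1: "OS is defined as the time from randomization until death from any cause". Section 13.2 assigns OS to the intention-to-treat set, that is, all randomized participants.

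Survival information is gathered separately from imaging. Section 1.1 says "All participants will be followed by telephone contact or medical record review for overall survival until death", or until consent is withdrawn or the study ends. Study Calendar footnote 10 sets the interval: "participants will be followed every 3 months (+/- 1 month) via contact or medical record review until death". Footnote 31 adds "Date of death and reason should be collected for overall survival purposes, when applicable".

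For PFS, Section 11 has its own rule: "For participants who do not progress or die, PFS will be censored at the last adequate radiologic assessment". Section 11.2.4(e) counts a failure to return because of death or deterioration as progression.

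**The concern.** The rule has two separate triggers, and meeting either one is enough. A participant can have a recorded date of death, and so have survival data, yet still meet the first trigger for want of an efficacy assessment. Nothing in the sentence says that the death takes precedence.

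Such participants can arise under this design. The intention-to-treat set keeps people who never receive the pre-operative infusion, never have surgery, or die soon after surgery. Response assessment first appears in the Study Calendar at the pre-adjuvant visits, weeks after randomization.

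At stake is the OS estimate in small arms, where one or two participants move the curve visibly. Section 13.4 sets OS against historical data; there, handling the trial's own arms alike would not cancel a distortion. The between-group OS analyses in Section 13.6 state no other rule. As the sentence can be programmed in more than one way, the choice could end up being made after the data are seen.

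**Working it through.** The plan states no figure on this point to reproduce. The check has three parts: the text, the time at risk, and the size of the effect for assumed counts.

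**1. What each reading does to a participant with a known death and no scan or response assessment**

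| Reading of *efficacy evaluation data* | Treatment of the death | Consistent with Section 13.1.1? |
|---|---|---|
| A scan or response assessment | Censored at Day 1 | No |
| Any efficacy endpoint, including a date of death (OS is listed under Efficacy Endpoints) | Event on its date | Yes |
| Death before evaluation counts as an efficacy result (progression under 11.2.4(e)) | Event on its date | Yes |
| Endpoint by endpoint: efficacy data for PFS, survival data for OS | Event on its date | Yes |

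The text does not choose between these rows.

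**2. When the first post-surgery assessment falls**

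- Infusion: 0 to 5 days after randomization (Section 5.3.1).
- Surgery: 21±7 days later, so 14 to 28 days.
- First post-surgery cycle: 28 to 35 days after surgery (Section 5.1).
- Earliest: 0 + 14 + 28 = 42 days. Latest: 5 + 28 + 35 = 68 days.

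Footnote 25 confirms the start of the imaging series: "On-study imaging should be performed every 6 weeks starting from post-surgery treatment Cycle 1 Day 1". On the first reading, deaths in roughly the first 42 to 68 days are therefore the ones exposed. The documents do not say how many to expect.

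**3. Size, for assumed counts**

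Let n be the arm size, s the number truly alive at a given time, k the earlier deaths erased at Day 1, and m the participants alive at that time who are also dropped at Day 1. With complete follow-up of everyone else,

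apparent survival = (s − m) / (n − k − m), against a true value of s / n.

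Take n = 15, the planned evaluable number per arm. For s, assume 5 or 8 alive at 12 months. These are the counts from 15 evenly spaced exponential survival times with the medians of 224 and 414 days quoted in Section 2.2.2. The exponential shape and the values of k and m are assumptions.

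| | k = 0 | k = 1 | k = 2 | k = 3 |
|---|---|---|---|---|
| s = 5, m = 0 | 5/15 = 33.3% | 5/14 = 35.7% | 5/13 = 38.5% | 5/12 = 41.7% |
| s = 5, m = 1 | 4/14 = 28.6% | 4/13 = 30.8% | 4/12 = 33.3% | 4/11 = 36.4% |
| s = 8, m = 0 | 8/15 = 53.3% | 8/14 = 57.1% | 8/13 = 61.5% | 8/12 = 66.7% |

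For Groups A and B pooled (n = 30, s = 10, m = 0), the values are 10/30 = 33.3%, 10/29 = 34.5%, 10/28 = 35.7% and 10/27 = 37.0%.

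Setting the apparent value equal to s/n gives m = k·s/(n − s). With s = 5 and n = 15 this is m = k/2, so one dropped survivor offsets two erased deaths exactly. Below that ratio the estimate is too high, and above it too low.

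The Kaplan-Meier median (first time the curve is at or below 50%), with n = 15 and m = 0:

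- k = 0: the 8th death (7/15 = 46.7% remain).
- k = 1: still the 8th death (7/14 = 50%).
- k = 2: the 9th death (6/13 = 46.2%).
- k = 3: the 9th death (6/12 = 50%).

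Under the 224-day exponential assumption, the step from 8th to 9th death is 224 to 270 days.

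**The case against.** The strongest reply is that the damaging reading is not the natural one. Section 13.1.1 lists OS among the efficacy endpoints, so a participant with a recorded death has efficacy data. Or the sentence was meant endpoint by endpoint and was worded too briefly. On either view no death is lost. This stands as an account of what may have been intended, and it is why the number affected may be zero. It does not settle the matter: the rule sits in the OS paragraph, uses 'or', and does not state the intention.

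Four stronger readings are tempting, and the documents do not support them.

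- *The rule also breaks the intention-to-treat set and the follow-up provisions.* A participant censored at Day 1 is still in the intention-to-treat set. Section 1.1 and footnote 31 govern follow-up and data collection, not analysis. The real contradiction is with the definition of OS in Section 13.1.1.
- *The rule makes OS look better.* That follows only if deaths alone are removed. Participants alive without an efficacy assessment would be dropped as well, and they pull the other way. The direction of any difference between arms is likewise unknown.
- *Living participants have no usable censoring date.* No sentence states that they are censored when last known alive, but contact every 3 months is planned, and Section 5.10 requires the date of leaving the study to be recorded. Ordinary practice would fill this gap; it is mostly missing detail.
- *Day 1 could mean Day 1 of a post-surgery cycle.* Elsewhere the schedule ties the term to a cycle. Here it stands alone, in a paragraph on an endpoint whose clock starts at randomization. A definition would help, but the strained reading is not the problem.

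The stakes are also limited: Section 13.4 names no test or alpha level for OS, and the log-rank comparisons in Section 13.6 are exploratory.

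**Conclusion.** The point holds in a limited form. The plan's only OS censoring sentence can, on a reading that its words allow, remove a known death from the OS curve at Day 1. That contradicts OS as death from any cause, and no other passage overrides it.

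The size cannot be fixed from the documents. The tables show what one to three erased deaths would do in an arm of 15 under assumed counts; they do not predict that any will occur. The net direction depends on how many living participants the same rule removes. The conclusion concerns the OS estimates in Sections 13.4 and 13.6 only; the primary TIL density analysis is unaffected. The sentence should be replaced before OS data are analysed, because it is a stated rule that can give a wrong result.

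**What to change.** Replace the sentence in Section 13.4 with an OS rule that:

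1. drops the efficacy-data condition altogether;
2. counts every known death as an OS event on its date, whatever assessments were made;
3. censors all other participants at the date last known alive;
4. censors at randomization, named as such, only participants with no survival information after randomization;
5. applies equally to the OS analyses in Section 13.6.

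If a rule is wanted for participants with no scan, on which Section 11 is silent, write it separately for PFS. It should be consistent with Section 11 and Section 11.2.4(e), and tied to the PFS time origin. Randomization should not be carried over as that origin without thought. The only origin stated for a PFS endpoint is surgery (PFS6, Section 13.1.1), at least 14 days after the pre-operative infusion, so censoring at randomization would fall before time zero.

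The cost is a few sentences, made by protocol amendment if OS counts as a key secondary hypothesis under the opening paragraph of Section 13. No new data are needed: dates of death and survival contacts every 3 months are already planned.
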